During these visits we will test the efficacy of pump therapy containing Xeris glucagon in the prevention and management of post-exercise hypoglycemia in up to 20 patients with PBH. If patients studied in Part 1 are recruited for Part 2, there will be at least a two-month interval between completion of Part 1 and initiation of Part 2.

Visit Day 1: Screening: We will recruit adult male or female patients with PBH from the hypoglycemia clinic at Joslin (directed by [name]). Patients will undergo a history and physical examination, with particular emphasis on inclusion and exclusion criteria. Blood and urine samples will be obtained for screening laboratory testing including hemoglobin A1c, CBC, comprehensive chemistry, urinalysis, and pregnancy test (if applicable). An electrocardiogram will be obtained and reviewed during the visit by the study physician. Consent forms will be reviewed in detail with potential participants. Patient comfort, skill, and independence with sensor insertion will be determined at this visit and reassessed at subsequent visits.

Visit Day 2 (Optional): CGM Sensor Placement: Two continuous glucose monitor sensors (Dexcom) will be placed on the anterior abdominal wall two days prior to visit 3 (to ensure sensor availability and calibration for subsequent visit day 3) and will be blinded during the intervals between patient visits. Participants will be provided a glucometer and instructed in both sensor insertion and calibration techniques. This visit, with sensor placement, may occur concurrent with visit 1 if visit 3 can be scheduled within 2 days of visit 1/2. Alternatively, this visit can be substituted with a phone call if the patient has prior experience with sensor insertion and calibration and is comfortable with this approach. During the call, a study physician will discuss what medications, activities and food adjustments need to be made in anticipation of visit day 3 and will record timing of the sensor placements.

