Visit Day 3: Exercise Protocol: The exercise protocol to be employed [35] will consist of cycling on a stationary bicycle ergometer in the clinical research center. Subjects will be counseled to avoid vigorous exercise for 24 hours before testing. Participants will arrive in the morning after an overnight (>12 hour) fast. Two intravenous lines will be inserted for blood sampling and to provide intravenous access. Two plasma glucose values greater than 75 mg/dL used to calibrate the sensors will be required to initiate the exercise study visit. Placement of the Dexcom sensors will be verified, and calibration will be performed using at least 2 venous blood glucose samples (YSI) obtained 15 minutes apart. A Garmin Foot Pod accelerometer will be applied. An EKG will be obtained and reviewed by a licensed provider prior to initiation of exercise. An OmniPod® containing glucagon will be inserted, with settings to deliver a dose of 300 µg of glucagon when an alarm is triggered by the controller algorithms which predict a glucose value <75 mg/dl.

Vital signs, including pulse, blood pressure, heart rate, and oxygen saturation will be assessed at baseline and every 2.5 minutes during exercise. Two baseline blood samples will be obtained for measurement of plasma glucose (YSI) immediately, and for subsequent hormonal assays. At time 0, low intensity cycling will be initiated; at time 5 minutes, intensity will be increased at 1 minute intervals until patient reaches target heart rate and will be continued until patient is exhausted, maximum heart rate is reached ($220 - (\text{age} \times 0.7)$), or total duration of exercise of 15 minutes is achieved. After exercise is completed, the subject will be returned to the supine position, post-exercise labs will be drawn and glucose levels will be assessed every 10 minutes for up to 180 minutes. Additional labs including insulin, glucagon, and incretins will be drawn at 10, 30, 60, 90 and 120 minutes after exercise.

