Exercise will be halted immediately if the participant develops chest pain or chest pressure, undue shortness of breath, hypotension, feelings of being unwell, signs of poor perfusion (e.g., lightheadedness, confusion, ataxia, pallor, cyanosis, nausea, cold and clammy skin, etc.), heart rate above the prespecified maximum heart rate of the subject (MHR), drop in systolic or diastolic blood pressure by more than 20 mm Hg as compared with baseline, or if the participant chooses to stop. In addition at any point during the study visit, if the participant develops severe nausea, abdominal pain or feels the need to stop, they will be able stop the procedure.

As in part 1, the closed-loop system will be set to use both the post-bariatric hypoglycemia algorithm and classic algorithm to predict hypoglycemia below a threshold of 75 mg/dl. Once a hypoglycemic event is predicted this will trigger a pump-delivered bolus of glucagon or vehicle, with the goal of preventing further decline in glucose values. If the sensor glucose value is ≤ 75 mg/dL then 6 units (equivalent volume to 300 µg of glucagon) of glucagon or vehicle will be delivered; if automated delivery of glucagon by the pump is not yet available at the time of these studies, manual dosing of the test compound will be performed by the study physician, as guided by the algorithm.

If the closed-loop system generates a second hypoglycemia alarm after a lockout period (15 minutes for sensor glucose ≤ 60 mg/dL and 30 minutes for >60 mg/dL), then the closed-loop system will deliver a second dose of study drug as noted in part 1.

Plasma glucose will be measured (YSI) at 5 minute intervals for 30 minutes and then every 15 minutes for two hours after treatment to ensure successful treatment. Glucagon and insulin levels will be analyzed concurrently at time of hypoglycemia prediction alarm as well as 30 minutes and 60 minutes following treatment bolus to determine the magnitude of increase above baseline. Lunch will be provided 120 minutes after glucagon treatment.

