As in part 1, if the glucose level falls at or below 55 mg/dl (i.e. as a result of vehicle delivery on vehicle treatment days, inadequate trigger, or inadequate pump-delivered glucagon response), or if the patient develops neuroglycopenia or discomfort with signs and symptoms of hypoglycemia then the closed-loop system will be deactivated and the treatment protocol for clinically significant hypoglycemia will be initiated followed by administration of a standard lunch meal (as described in part 1).

Thirty minutes after glucagon treatment, the Omnipod® pump will be removed and the site will be assessed visually using the Draize scale. Following the standard lunch meal, venous blood glucose will

Approved by

JDC CHS

be monitored every 15 minutes for a minimum of 2 hours and then every 30 minutes until the time of discharge. The time of discharge will be set at 6 hours after the exercise is stopped to ensure stability prior to discharge from the clinical research unit. Prior to discharge, the plasma glucose (measured by YSI) must be between 80 and 200 mg/dL on the final two measurements, taken at least 30 minutes apart. If the plasma glucose is between 80 and 90 mg/dL then the CGM trend arrow must be either stable or increasing during the last 30 minutes of observation.

Prior to discharge, the sensors will be removed to permit analysis of timing of alerts and the site of the Omnipod insertion will be reassessed using the Draize scale. Accelerometry data will be used as an input for future integration and modification of the algorithm. Blood samples collected during this visit will be processed and stored at -80 for subsequent analysis of insulin, glucagon and incretin hormone levels in response to exercise and treatment. The patient will be called by a study team member within 24 hours of the study visit to collect data for symptoms, glucose values, and any adverse events following study visit.

Hardware Cleaning:

Equipment that touches intact skin will be cleaned prior to and after each use, using methods suggested by manufacturer, including Clorox Healthcare 35309 Germicidal Wipes.

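### Part 2 does not reconcile its control: one exercise visit is scheduled, with no allocation to vehicle shown, yet its text and the primary endpoint refer to vehicle

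*Combined protocol and SAP*

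**What the plan says.** Part 2 opens with "During these visits we will test the efficacy of pump therapy containing Xeris glucagon in the prevention and management of post-exercise hypoglycemia". The ceiling for this Part is 20 participants. It lists Visit Day 1 (screening), an optional Visit Day 2 (sensor placement) and Visit Day 3 (exercise). The text then turns to hardware cleaning.

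Within Visit Day 3:

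- **Pump contents.** The OmniPod "containing glucagon will be inserted, with settings to deliver a dose of 300" µg when the algorithm alarms.
- **Bolus.** "Once a hypoglycemic event is predicted this will trigger a pump-delivered bolus of glucagon or vehicle". The sentence on bolus volume repeats the same two alternatives.
- **Rescue.** Glucose may fall "as a result of vehicle delivery on vehicle treatment days".
- **Timings.** "Lunch will be provided 120 minutes after glucagon treatment", and the pump comes off "Thirty minutes after glucagon treatment".
- **Stored samples.** They are kept to measure "hormone levels in response to exercise and treatment", with no split by type of delivery day.

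Part 1 is explicit where Part 2 is not. Its Study Visit Day 5 repeats Visit 3 with the treatment not yet given, one to two weeks later, and its sampling text separates vehicle days from glucagon days.

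Section 4 (Data Analysis) sets one primary endpoint covering meal and exercise provocation, compared with vehicle, and three secondary comparisons of glucagon with vehicle. The statement that 28 subjects are randomized, the 12-of-20 success rule and the look after 10 paired completers do not say which Part they apply to.

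Section 6 (Glucagon Infusion System) describes the pump as filled with glucagon and, in the next sentence, allows it to deliver either glucagon or vehicle.

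**The concern.** Exercise is provoked only in Part 2, so the exercise component of a vehicle-controlled primary endpoint has to come from there. The listed schedule has one exercise visit, and the documents do not show who would receive vehicle at it, or when.

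The choice of design determines what can be estimated: a within-participant contrast, a between-participant contrast, or no contrast with vehicle. If exercise visits are run without the control that Section 4 assumes, no later analysis can supply it. The three secondary comparisons have the same gap for exercise. If vehicle is given in Part 2, the lunch and pump-removal timings also lack a stated starting point on a vehicle day.

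**Working it through.** **1. The plan's own figure.** Section 4 gives 40 screened, 30% ineligible and 20% dropout.

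- 40 × (1 − 0.30) = 28, which matches the stated 28 randomized.
- 28 × (1 − 0.20) = 22.4 expected completers, against a goal of 20.

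The count reproduces. It does not say what the 28 are randomized to in Part 2, so it neither supports nor weakens the point.

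**2. Test visits per participant.** Part 1 has two (Visits 3 and 5). Part 2 has one (Visit 3).

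**3. Pairs available.** Per participant, pairs = min(glucagon visits, vehicle visits). With one visit this is min(1, 0) or min(0, 1), which is 0 either way. Over up to 20 participants: 20 × 0 = 0 pairs. This holds whichever sentence governs the pump contents.

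**4. What each reading yields, at 20 participants.**

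| Reading | Glucagon visits | Vehicle visits | Pairs | Exercise comparison with vehicle |
|---|---|---|---|---|
| Pump-contents sentence governs, one visit | 20 × 1 = 20 | 20 × 0 = 0 | 0 | Cannot be estimated |
| Bolus sentence governs, one visit each | Split not stated; both columns sum to 20 | Split not stated | 0 | Unpaired only |
| Crossover, with a visit that is not listed | 20 | 20 | 20 | Paired; 40 visits in all |

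**5. Does any reading fit all the text?** No.

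- A single glucagon visit conflicts with the bolus and rescue wording in Part 2 and with the exercise component of the Section 4 endpoint.
- A parallel comparison conflicts with the literal pump-contents sentence, fits poorly with the rescue text's mention of vehicle days, and has no stated Part 2 allocation.
- A crossover needs a visit that is not scheduled. The references back to Part 1 within Visit Day 3 concern the algorithm, second-dose and rescue rules, not the visit schedule.

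**6. Do the minor clues decide it?** No.

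- The plural in the opening sentence can include screening and sensor placement.
- The rescue phrase about vehicle days also appears word for word in Part 1, so it may be carried over.
- The visit 5 stipend in Section 11 names no Part and fits Part 1.
- Section 6 gives maximum blood volumes of 450 ml for Part 1 and 338 ml for Part 2. If 450 ml covers two equal visits (an assumption), that is 450 / 2 = 225 ml each. For Part 2 the figure is 338 ml if there is one visit, or 338 / 2 = 169 ml each if there are two. The number of visits covered is not stated.

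**The case against.** The strongest reply is that the protocol uses the word glucagon loosely. Section 6 calls the pump glucagon-filled for the whole study and at once allows vehicle delivery. It also describes monitoring after glucagon delivery and lunch without limiting this to one Part. On that view, the Visit Day 3 pump sentence and the two timings counted from glucagon treatment may be shorthand for study drug. This stands: the pump sentence alone cannot establish the design.

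A second reply is that one exercise visit with either glucagon or vehicle could be a parallel comparison, since Section 4 speaks of randomized subjects just after naming both Parts. This also stands as a possible reading, although Part 2 states no allocation.

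A third reply is that some early text and part of the Part 1 description were not available for review, and a general statement on allocation or order may be there. That is fair. Such a statement could show the intent. It would not remove the conflict within the Part 2 text, which reads continuously from its heading to the hardware section.

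A reader might infer that Part 2 has no vehicle control and that no vehicle exercise data will be collected. The documents do not support that. It follows only if the pump-contents sentence overrides the bolus and rescue wording of the same visit.

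**Conclusion.** The point holds as an unreconciled control in Part 2, and it needs correcting because it touches the primary endpoint. As listed, 0 of up to 20 participants can provide a paired glucagon-vehicle exercise comparison. This rests only on the count of one exercise visit.

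The figure of 0 vehicle exercise visits, and with it the loss of the exercise comparison in the primary and all three secondary outcomes, is one branch and assumes that the pump-contents sentence governs. If the bolus sentence governs with one visit each, an unpaired comparison remains possible. Confidence is high that the wording conflicts. It does not extend to which design was intended, or to a conclusion that vehicle data will be absent. Part 1's paired meal comparison is not affected.

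**What to change.** Reconcile the Part 2 text and the Section 6 pump description with Section 4 by stating which design applies.

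- **(a) Paired.** Show the vehicle exercise visit in the Part 2 schedule, with pump contents at each visit, order and interval. Reconcile the timings counted from glucagon treatment with the bolus wording that allows vehicle.
- **(b) Parallel.** State the Part 2 allocation and say that the exercise comparison is between participants. Limit the paired analysis in Section 4 to Part 1.
- **(c) Single glucagon visit.** Restrict the vehicle-controlled primary endpoint, the 12-of-20 rule, the paired interim look and the three glucagon-versus-vehicle secondary comparisons to Part 1. Report Part 2 descriptively and correct its vehicle wording.

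**Cost.** Wording only, if the stated design is the one already planned. Option (c) gives up the vehicle-controlled claim for exercise. Adding a vehicle visit that was not planned is not the cheap option: it means up to 20 further exercise visits (40 instead of 20). The protocol says "The time of discharge will be set at 6 hours after the exercise is stopped", so those visits carry up to 20 × 6 = 120 further hours of post-exercise observation.

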3. INCLUSION / EXCLUSION CRITERIA

Screening: We will recruit adult male or female patients with PBH from the hypoglycemia clinic at Joslin (directed [name]). Patients will undergo a history and physical examination, with particular emphasis on inclusion and exclusion criteria. Blood and urine samples will be obtained for screening laboratory testing including hemoglobin A1c, CBC, comprehensive chemistry, and urinalysis. Consent forms will be reviewed in detail with potential participants.

Inclusion criteria:

1. Males or females diagnosed with ongoing post-bariatric hypoglycemia with prior episodes of neuroglycopenia, unresponsive to dietary intervention (low glycemic index, controlled carbohydrate portions) and trial of acarbose therapy at the maximally tolerated dose.
2. Age 18-65 years of age, inclusive, at screening.
3. Willingness to provide informed consent and follow all study procedures, including attending all scheduled visits.

Exclusion criteria:

1. Documented hypoglycemia occurring in the fasting state (> 12 hours fast);
2. Chronic kidney disease stage 4 or 5 (including end-stage renal disease);
3. Hepatic disease, including serum ALT or AST greater than or equal to 3 times the upper limit of normal; hepatic synthetic insufficiency as defined as serum albumin < 3.0 g/dL; or serum bilirubin > 2.0;
4. Congestive heart failure, NYHA class II, III or IV;
5. History of myocardial infarction, unstable angina or revascularization within the past 6 months or 2 or more risk factors for coronary artery disease including diabetes, uncontrolled hypertension, uncontrolled hyperlipidemia, and active tobacco use;
6. History of cardiac arrhythmia or arrhythmia detected by EKG during the screening visit;
7. History of syncope (unrelated to hypoglycemia) or diagnosed cardiac arrhythmia
8. Concurrent administration of β -blocker therapy;
9. History of a cerebrovascular accident;
10. Seizure disorder (other than with suspect or documented hypoglycemia);
11. Active treatment with any diabetes medications except for acarbose;
12. Active malignancy, except basal cell or squamous cell skin cancers;
13. Personal or family history of pheochromocytoma or disorder with increased risk of pheochromocytoma (MEN 2, neurofibromatosis, or Von Hippel-Lindau disease);
14. Known insulinoma or glucagonoma;
15. Major surgical operation within 30 days prior to screening;
16. Hematocrit \leq 33%;
17. Bleeding disorder, treatment with warfarin, or platelet count <50,000;

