Exercise Intervention: There is a remote possibility of adverse events including hypoglycemia, abnormal blood pressure, fainting, dizziness, arrhythmia, and in very rare instances, heart attack or stroke. There also exists the risk of bodily injury including injuries to muscles, ligaments, tendons, and joints. To minimize the risk of an adverse event, all participants will be pre-screened by the study physician prior to participation. Specific attention will be focused on history of known cardiac arrhythmias, cardiovascular, cerebrovascular disease or concurrent β -blocker therapy. Participants will be excluded if these conditions are present.

At least one study physician and one study nurse will be present during the exercise portion with careful monitoring of glucose, vital signs and symptoms. The minimum plasma glucose level prior to initiating the exercise should be greater than 75 mg/dl. Exercise will take place on a stationary bicycle which has a low impact on joints and low risk for falls or trauma. Patients will exercise until a threshold of the sensation of exhaustion, max heart rate of $(=208 - (0.7 \times \text{age}) \text{ bpm})$ or 15 minute duration is achieved. Exercise will be halted immediately if the participant develops chest pain or chest pressure, undue shortness of breath, hypotension, feelings of being unwell, signs of poor perfusion (e.g., lightheadedness, confusion, ataxia, pallor, cyanosis, nausea, cold and clammy skin, etc.), Heart rate above the prespecified maximum heart rate of the subject (MHR), drop in systolic or diastolic blood pressure by more than 20 mm Hg as compared with baseline, or if the participant chooses to stop. The study visit will also be halted if the participant develops unremitting nausea, abdominal pain, or wishes to discontinue the study for any reason. In case of an emergency, an emergency medical team will be available on-site at the Joslin Diabetes Center to stabilize the patient prior to transport to Beth Israel Deaconess Medical Center if needed.

Screening Tests and Procedures: It is possible that as a result of the screening process a subject may learn that they have a health disorder that they were unaware they had. Every effort will be made to help the participant obtain the care that they need.

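### The maximum heart rate that ends the Part 2 exercise test is defined by two formulas that differ by 12 bpm at every age

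*Combined protocol and SAP*

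**What the plan says.** The limit is described in two places, both in current protocol text.

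- **Part 2, Visit Day 3: Exercise Protocol.** Cycling starts at low intensity and is stepped up each minute from minute 5. It goes on "until patient is exhausted, maximum heart rate is reached ($220" − (age × 0.7), or 15 minutes of exercise are completed.
- **Section 6, Possible Risks, Exercise Intervention.** The same stationary-bicycle test is described as follows: "Patients will exercise until a threshold of the sensation of exhaustion, max heart rate of $(=208 - (0.7" × age) bpm, or 15 minutes.

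Each section then lists reasons to halt at once. The procedure includes "heart rate above the prespecified maximum heart rate of the subject (MHR") and the risk section repeats it: "Heart rate above the prespecified maximum heart rate of the subject (MHR"). Neither halting sentence carries a formula or a cross-reference.

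Section 3 sets the ages to which the limit applies: "Age 18-65 years of age, inclusive, at screening".

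**The concern.** A maximum heart rate is one number per participant. Here it is both an end condition of the exercise test and a trigger for an immediate halt, and the protocol supplies two values for it. The procedure text, which staff would be expected to work from, carries the higher value. The risk section, which explains how participants are protected, carries the lower one.

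At stake is a safety threshold in a test for which the protocol itself lists arrhythmia, fainting and, very rarely, heart attack or stroke as possible harms. With two limits in force, two members of staff could act differently on the same reading, and it would be unclear which action was a protocol deviation.

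**Working it through.** **Inputs**

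- Procedure formula (Part 2, Visit Day 3): 220 − 0.7 × age.
- Risk-section formula (Section 6, Exercise Intervention): 208 − 0.7 × age.
- Eligible ages (Section 3): 18 to 65.

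The document gives no worked bpm value, so there is no stated figure to reproduce.

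**Difference**

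(220 − 0.7 × age) − (208 − 0.7 × age) = 220 − 208 = 12 bpm. The age terms cancel, so the gap is constant. Evaluating both formulas at every whole year from 18 to 65 gave 12.0 each time.

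| Age | Procedure (bpm) | Risk section (bpm) | Gap (bpm) | Gap as % of lower limit |
|---|---|---|---|---|
| 18 | 220 − 12.6 = 207.4 | 208 − 12.6 = 195.4 | 12 | 12/195.4 = 6.1% |
| 45 | 220 − 31.5 = 188.5 | 208 − 31.5 = 176.5 | 12 | 12/176.5 = 6.8% |
| 65 | 220 − 45.5 = 174.5 | 208 − 45.5 = 162.5 | 12 | 12/162.5 = 7.4% |

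**On the age scale**

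Both formulas fall by 0.7 bpm per year, so 12 bpm corresponds to 12/0.7 = 17.1 years. The procedure gives a 65-year-old the ceiling that the risk section gives someone aged about 48 (65 − 17.1 = 47.9).

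**Where the two rules conflict**

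At age 45 the risk section has reached its limit and the procedure has not for any heart rate from 176.5 up to 188.5 bpm. A reading of 180 bpm falls in that band.

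**Could a misprint reconcile them?**

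If the bracket in the procedure were misplaced and (220 − age) × 0.7 were meant, the limit would be 202 × 0.7 = 141.4 bpm at 18, 175 × 0.7 = 122.5 at 45 and 155 × 0.7 = 108.5 at 65. These still disagree with the risk section. The procedure also refers to a target heart rate, but that is a separate term with no formula and does not explain the difference.

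**The case against.** The strongest reply is that this is a drafting slip with little practical reach.

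- **Each section can be read as defining its own maximum.** A formula stands shortly before each halting rule. That is fair as a reading of each section alone, but it leaves two sections prescribing different limits for one test.
- **Many other safeguards apply.** Exercise is capped at 15 minutes, starts at low intensity, and stops at exhaustion. Vital signs are taken every 2.5 minutes and an EKG is reviewed beforehand. Symptoms, a blood-pressure drop of more than 20 mm Hg or the participant's wish also stop it. A physician and a nurse are present, and Section 3 excludes much cardiac disease. This stands as a limit on the consequence: the discrepancy matters only for someone inside the 12 bpm band with no other stopping condition met, and the document does not show how often that would happen. But heart rate is listed as a trigger in its own right and should work when nothing else does.
- **A value may be set for each participant on a worksheet that is not in the document.** This is possible, since the wording implies a value fixed in advance. Whoever sets it would still have to choose between the two formulas.
- **The intended formula is unknown.** This stands. The exercise protocol is taken from a cited source not available here, so preferring the lower limit is a protective default, not a finding about what was meant.
- **A lower ceiling could weaken the provocation.** Exercise is the stimulus in Part 2, and earlier stopping might blunt it. The document gives no basis for sizing this.

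**Conclusion.** The concern holds. One safety limit has two values, 12 bpm apart at every eligible age (6.1% to 7.4% of the lower limit), and nothing in the document resolves them. The procedure carries the more permissive value.

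The conclusion rests only on the two printed formulas and on both describing the same test, which the shared end conditions and the bicycle setting make clear. It assumes nothing about how often participants reach the band between the limits. The practical consequence is bounded by the other stopping rules, and no effect on the analysis is asserted. It should still be corrected, because staff must be able to apply a halting rule without choosing between two numbers.

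**What to change.** In Part 2, Visit Day 3: Exercise Protocol, replace 220 − (age × 0.7) with 208 − (0.7 × age). The end condition and the immediate-halt rule in both sections then rest on one limit, the lower of the two already in the protocol. If the sponsor has grounds for the higher formula, it should state them and align the risk section instead. The two sections must not continue to differ. The vital-sign schedule (baseline and every 2.5 minutes) can stay as it is.

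The cost is one edited formula, with no added equipment, visits or readings. Some tests may end slightly earlier than under the higher ceiling. The undefined target heart rate in the same paragraph is a separate gap that this edit does not close.

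### Part 2 sets two heart-rate stop limits 12 bpm apart, and removes the pump just as a second dose above 60 mg/dL becomes allowed

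*Combined protocol and SAP*

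**What the plan says.** **Heart-rate limit.** Under Part 2, Visit Day 3: Exercise Protocol, cycling continues until exhaustion, 15 minutes, or the point where "maximum heart rate is reached ($220" minus 0.7 × age. Section 6 (Possible Risks), Exercise Intervention, describes the same test and gives a "max heart rate of $(=208 - (0.7" × age. Both places also list reasons to stop at once. In the Part 2 visit text one of these is "heart rate above the prespecified maximum heart rate of the subject (MHR"), with no formula beside it.

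**Second dose.** In Part 2 the two algorithms "predict hypoglycemia below a threshold of 75 mg/dl", and an alarm triggers a bolus. A second alarm can be acted on after "a lockout period (15 minutes for sensor glucose ≤ 60 mg/dL and 30 minutes for >60 mg/dL"), and "then the closed-loop system will deliver a second dose of study drug as noted in part 1". Part 1 accepts a second alarm at any time in a two-hour observation period once the lockout has passed, and removes the pump when the standard meal is eaten. Part 2 differs: "Thirty minutes after glucagon treatment, the Omnipod® pump will be removed". Lunch in Part 2 comes 120 minutes after treatment.

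**The concern.** These are two separate contradictions in the current Part 2 text.

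First, a safety stop has two values. Staff who follow the visit procedure and staff who follow the risk section would act differently on the same reading. At age 40, a participant at 185 bpm must stop under one and may continue under the other.

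Second, the pump leaves at the moment a second dose above 60 mg/dL first becomes possible. The primary endpoint in Section 4 is prevention of glucose below 65 mg/dL. Because the alarm predicts a fall below 75, a second alarm can occur while glucose is still 65 or above and the endpoint can still be met. That is where a repeat dose matters most, and it is largely ruled out. Once glucose is below 65 the endpoint is already missed, and a second dose could only limit further decline before rescue at 55 or below. Part 2 would then test the system mostly without the repeat-dose feature that its own text describes.

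**Working it through.** The plan states no derived figure to reproduce. The check is direct arithmetic on its own inputs.

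**Heart-rate limits**

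Inputs: 220 − 0.7 × age (Part 2, Visit Day 3); 208 − 0.7 × age (Section 6, Exercise Intervention); ages 18 to 65 (Section 3, inclusion criterion 2).

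Gap = (220 − 0.7 × age) − (208 − 0.7 × age) = 12 bpm at every age.

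| Age | Visit procedure (bpm) | Risk section (bpm) | Gap | Gap as % of lower limit |
|---|---|---|---|---|
| 18 | 207.4 | 195.4 | 12 | 6.1 |
| 40 | 192.0 | 180.0 | 12 | 6.7 |
| 65 | 174.5 | 162.5 | 12 | 7.4 |

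**Second-dose window, counted from the first dose**

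Inputs: lockout of 15 minutes (60 mg/dL or below) or 30 minutes (above 60); Part 2 pump removal at 30 minutes; Part 2 lunch at 120 minutes; Part 1 two-hour window.

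Window = last minute at which a dose is possible − lockout.

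| Sensor glucose | As written (pump off at 30) | Two-hour rule, pump on |
|---|---|---|
| Above 60 mg/dL | 30 − 30 = 0 min | 120 − 30 = 90 min |
| 60 mg/dL or below | 30 − 15 = 15 min | 120 − 15 = 105 min |

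The zero is effective rather than absolute, since a dose at exactly minute 30, or late removal of the pump, would get through. The 15-minute window is narrower in practice because the loop is switched off at glucose of 55 or below.

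**Which dose starts the removal clock?** Part 2 does not say whether it is the first or the latest dose. Above 60 mg/dL this changes nothing: no second dose is allowed before minute 30, so until then the first dose is also the latest.

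**Which sensor value sets the lockout?** The visible text does not say.
- If it is the value at the second alarm (an assumption), every second alarm at 65 or above carries the 30-minute lockout and has effectively no window. Part 1's dosing tiers from 65 to 150 mg/dL then cannot run in Part 2.
- If it is the value at the first dose, such an alarm could be served only in minutes 15 to 30, and only after a first dose at 60 or below.

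**Distance from alarm to endpoint:** 75 − 65 = 10 mg/dL.

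**The case against.** The strongest reply on heart rate is that the immediate-stop rule in the visit text follows directly after the 220 formula, so its natural referent is that formula. On that reading there is one conflict, between the visit text and Section 6, and not a third ambiguity. That is fair, but the one conflict remains. Practical risk is also limited. Exhaustion, the 15-minute cap, and the symptom and blood-pressure stops all apply. Section 3 excludes arrhythmia, recent cardiac events and beta-blocker use, an EKG is reviewed before exercise, and "At least one study physician and one study nurse will be present during the exercise portion". No harm is shown.

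On dosing, Part 2 lets the physician dose manually, guided by the algorithm. That clause applies only if automated delivery is not yet available, and it says nothing about dosing after the pump is off. It can also be said that Part 2 imports Part 1's two-hour window by reference. It does, but the removal sentence then defeats it. Table 1, to which Part 1 refers for second-dose volumes, was not in the text available to this review and may settle which sensor value governs the lockout. That affects only the assumption labelled above.

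Participants are not left untreated: Section 6 provides glucose tablets and standard glucagon if hypoglycemia develops despite pump delivery. That is clinical care, not the repeat dose under test.

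Two limits stand in full. The documents give no frequency for second alarms or for reaching either heart-rate limit, so no effect on the endpoint result can be calculated. And neither item changes the sample size or the analysis.

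**Conclusion.** Both inconsistencies hold and should be fixed. The exercise stop limit has two values 12 bpm apart at every eligible age, and the documents do not settle which is right. The second-dose window in Part 2 is effectively 0 minutes above 60 mg/dL and about 15 minutes at 60 or below, against a two-hour window with the pump in place in Part 1. The heart-rate gap and the window lengths follow directly from the text. Only the split by sensor value at the second alarm rests on an assumption. How often either problem would bite is unknown.

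**What to change.** **Heart rate.** Use 208 − 0.7 × age, the more conservative limit, in the visit procedure, the immediate-stop rule and Section 6. Some participants may stop slightly earlier.

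**Second dose.** Keep the Part 2 pump in place until the standard lunch, as in Part 1, and state the two-hour window in the Part 2 text. Carry over Part 1's lunch rule: 120 minutes after the first dose or 30 minutes after the second, whichever is later. Also state when the pump comes off if no alarm occurs, since Part 2 times lunch only from treatment.

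**Costs**
- Pump wear: 120 − 30 = 90 minutes longer, or up to 150 − 30 = 120 minutes if the second dose comes near minute 120 and lunch at 150. The first site assessment moves later with it, and lunch may be up to 30 minutes later.
- Discharge: for a first dose t minutes after exercise, the two-hour post-lunch minimum now fits the 6-hour discharge time if t + 120 + 120 ≤ 360, so t ≤ 120. With the latest lunch it needs t + 150 + 120 ≤ 360, so t ≤ 90. The text should let discharge move later.
- Blood: if Part 1's sampling after a second dose carries over, there are at most 30 / 5 = 6 extra glucose draws, with insulin and glucagon analysed concurrently. Some may coincide with draws already scheduled. Volume per draw is not given; at an assumed 1 to 5 ml this is 6 to 30 ml, or 1.8% to 8.9% of the 338 ml Part 2 maximum. The documents do not say whether the 338 ml already allows for a second dose, so the total should be checked.
- Approvals: an amendment with the committee's prior agreement, and possibly review of the longer pump wear under the IDE. No added participants or visits.
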